**7.4 Cetuximab Dose Levels and Modifications**

	Starting Dose	Dose Level –1	Dose Level –2
Cetuximab	400 mg/m  (day 0) 250 mg/m  (day 7 and weekly during RT)	200 mg/m  (weekly)	150 mg/m  (weekly)

NOTE: Once the dosage of cetuximab has been decreased, it will remain at that level unless further dose reductions are required, at which time all dosages will remain at that level. Dosages CANNOT be increased once a dose reduction has taken place.

**7.4.1 Cetuximab Dose Modification for Hematologic Toxicity**

NCI CTCAE Toxicity Grade (CTCAE v. 4.0)	Cetuximab Dose a,b at Start of subsequent Cycles of Therapy
Neutropenia	
1 (1500-1999/mm  )	Maintain dose level
2 (1000-1499/mm  )	Maintain dose level
3 (500-999/mm  )	Decrease by 1 dose level with occurrence
4 (<500/mm  )	Decrease by 1 dose level with occurrence
Neutropenic Feverc	Decrease by 1 dose level
Thrombocytopenia	
1 (≥75,000/mm  )	Maintain dose level
2 (50,000- 74,999/mm  )	Maintain dose level
3 (25,000 – 49,000/mm  )	Decrease by 1 dose level with occurrence
4 (<25,000/mm  )	Decrease by 1 dose level with occurrence

aDose levels are relative to the starting dose in the previous cycle. Dose reductions of cetuximab below the –2 dose level will not be allowed.

bProvided that all the retreatment criteria are met (see section 7.4.5)

cOne reading of oral temperature ≥38.5°C and ANC ≤ 500

## 7.4.2 Cetuximab Dose Modification for Non-Hematologic Toxicity

NCI CTCAE Toxicity Grade (CTCAE v. 4.0)	Cetuximab Dose a,b,c,d
Fatigue (Asthenia) ≥ Grade 3	Decrease by 1 dose level
Nail changes (paronychia) Grade 2	Decrease by 1 dose level
Diarrhea Grade 3 despite maximal medical management	No dosage adjustment
Grade 3 recurrent, despite maximal medical management	Decrease by 1 dose level
Grade 4 despite maximal medical management	Decrease by 1 dose level
Headache	
≥ Grade 3	Decrease infusion rate by 50%
≥ Grade 3 despite decreased infusion rate and use of analgesic	Decrease dose by 1 dose level
Stomatitis/Mucositis	All patients are evaluated weekly. The dosage adjustments will be determined by the practicing clinicians at each visit. If a reduction is required, the dose will be decreased by 1 dose level. If > 2 dosage reductions are required, cetuximab will be discontinued.

aFor CTCAE Grade < 2 non-hematologic toxicity not described above, maintain dose level of drug.

bProvided that all the retreatment criteria are met as detailed in section 7.4.5.

cDose levels are relative to the previous dose. Dose reductions of cetuximab below the –2 dose level will not be allowed.

dIn any case of cetuximab treatment delay, there will be no reloading infusion, and all subsequent treatments will be at the assigned dose level.

### 7.4.3 Management of Cetuximab Hypersensitivity Reactions

CTCAE Grade	Hypersensitivity Reaction
Grade 1	Transient rash, drug fever <380C (<100.40F),
Grade 2	Urticaria, drug fever > 380C (> 100.40F), and/or asymptomatic bronchospasm
Grade 3	Symptomatic bronchospasm, requiring parenteral medication(s), with or without urticaria; allergy-related edema/angioedema
Grade 4	Anaphylaxis

7.4.3.1 Symptoms of hypersensitivity reactions should be managed per institutional chemotherapy infusion policy guidelines.

7.4.3.2 Study Therapy Retreatment Following Hypersensitivity Reactions: Once a cetuximab infusion rate has been decreased due to an allergic/hypersensitivity reaction, it will remain decreased for all subsequent infusions. If the subject has a second allergic/hypersensitivity reaction with the slower infusion rate, the infusion should be stopped, and the subject should receive no further cetuximab treatment. If a subject experiences a Grade 3 or 4 allergic/hypersensitivity reaction at any time, the subject should receive no further cetuximab treatment. If there is any question as to whether an observed reaction is an allergic/hypersensitivity reaction of Grades 1-4, the Principal Investigator or co-investigator should be contacted immediately to discuss and grade the reaction.

#### 7.4.5 Cetuximab Special Instructions

If cetuximab is omitted for more than four consecutive infusions for toxicity due to cetuximab, or for an intercurrent illness (e.g., infection) requiring interruption of therapy, the subject should be discontinued from further cetuximab therapy. If toxicities prevent the administration of cetuximab, the subject may continue to receive radiation therapy.

#### 7.4.5 Retreatment Criteria for cetuximab

Cetuximab may only be administered if all of the following criteria are met regardless of cycle, providing no criteria for discontinuation are met (see Section 10.0):

[figure not shown]
- Acne-like rash is ≤ Grade 2 (see Section 7.4.6)
- Grade 3 - 4 hematologic toxicities have resolved to ≤ CTC Grade 2

- Grade 3 - 4 non-hematologic toxicities have resolved to  $\leq$  CTC Grade 2, (except fatigue (asthenia), anorexia and alopecia)

7.4.6 Acne-Like Rash (rash acneiform or rash maculo-papular)

The dose of cetuximab will be adjusted for Grade 3 acne-like rash. The severity of these events will be graded according to the criteria for the CTC term “rash acneiform or rash maculo-papular.” The cetuximab dose alteration scheme is outlined in the figure below. If a subject experiences a Grade 3 acne-like rash (rash acneiform or rash maculo-papular), cetuximab therapy is to be held for up to four consecutive infusions (see table below). The Investigator could also consider concomitant treatment with topical and/or oral antibiotics; topical corticosteroids are not recommended. If there are subsequent occurrences of a Grade 3 acne-like rash (rash acneiform or rash maculo-papular), cetuximab therapy may again be omitted for up to four consecutive weeks. Treatment may resume with reduced doses of cetuximab if the skin toxicity has resolved to Grade 2 or less. Cetuximab dose reductions are permanent. Cetuximab will be discontinued if there is a subsequent occurrence of a fourth episode of Grade 3 acne-like rash (rash acneiform or rash maculo-papular) or there are more than four consecutive infusions held. The subject should be followed weekly until resolution of the rash. If a subject experiences a Grade 4 acne-like rash (rash acneiform or rash maculo-papular), cetuximab therapy will be discontinued.

Management of Cetuximab Acne-Like Rash

## **7.5** Evaluation of Response to Treatment

7.5.5 Careful evaluation of tumor extent will be recorded for both the primary tumor and regional nodes at specified intervals by the treating radiation oncologist, medical oncologist or otolaryngologist, who are co-investigators of the study.. CT-PET scans will be used at the discretion of the clinician to supplement clinical exams. However, it is not necessary for imaging abnormalities to revert to normal in order for a patient to be considered a clinical CR.

7.5.6 Biopsy of any persistent neck nodes is required at the 12-14 week post cetuximab-radiation laryngoscopy. Patients with any nodes initially > 3 cm in size who are CT-PET positive at 12-14 weeks post cetuximab-RT will undergo neck dissection. Patients whose CT-PET shows a complete response (CR) at 12 weeks post cetuximab-RT, will undergo clinical observation.

7.5.7 Diagnostic CT-PET scans may be obtained prior to scheduled endoscopies for tumor assessment.

7.5.8 Outpatient clinical examinations will be performed as comparable to clinical practice: at approximately 1 month following completion of RT and then approximately every 2 months during years 1 and 2. Clinical examinations will be performed by medical oncology, radiation oncology, and/or surgical oncology. To meet the examination requirements, patients need to be seen by at least one discipline (but not all three) during the aforementioned time intervals.

## **7.6** Evaluation of Toxicity and Quality of Life

7.6.5 Validated xerostomia-related and general quality of life questionnaires (Appendix C), and Common Toxicity Criteria Adverse Events (CTCAE, v.4) observer related items, will be collected before, during and after radiation therapy as indicated in the study calendar. As part of data collection related to the quality of life measures, pre and post-treatment employment status will also be recorded. Patients may be asked for this information during a clinic visit or contacted via phone. The study team will attempt to obtain this information from all enrolled patients.

## 8.0 Study Calendar

Assessment	Pre-Treatment*	Day 0 Loading Dose	Day 7	Weekly during RT†	1 mo post RT 	12-14 wks post RT 	Follow Up Years 1 and 2 
H&P/Physician Evaluation 	X			X	X	X	X
Research Biopsy	X**		X				
Dental Evaluation 	X						
COMP, Mg	X			X		X	
CBCP with diff	X			X		X	
CT-PET 	X					X	
CT or MRI of head/neck	X						
Toxicity Evaluation	X			X	X	X	X
QOL Questionnaire	X			end of treatment	X	X	X
Cetuximab		X		X			

\* The pre-treatment period is prior to the administration of the cetuximab loading dose. The pre-treatment toxicity evaluation and QOL Questionnaire may be completed at the time of consent. When a patient is determined eligible and enrolled, data will be used. If patient is not eligible or not enrolled, the data will not be used and the subject will be deemed a screen failure. The forms will be kept with the Informed Consent in the study record.

\*\* Research biopsy #1 must be within 4 weeks of loading dose (Day 0)

† Radiation therapy will start within approximately 4 days following Day 7 (+ or – a day) biopsy

Evaluations pre-treatment are by Radiation Oncology, Otolaryngology, and Medical Oncology. Evaluations weekly during RT are generally by Radiation Oncology via standard on-treatment notes. Evaluations in follow up will be by Radiation Oncology, Otolaryngology, and/or Medical Oncology. It is not necessary for patients to be seen by more than one discipline at each follow up visit.

Follow up: Examinations will be performed as comparable to clinical practice: at approximately 1 month following completion of RT and then approximately every 2 months during years 1 and 2. At approximately 12-14 weeks post-RT, patients will have clinical restaging performed for disease evaluation. A PET or MRI is acceptable for this restaging. Toxicity Evaluation and QOL Questionnaires will be collected at each of these visits. Biopsies, labs and imaging studies will be performed as clinically indicated. For years 3 - 5, all follow up will be as clinically indicated and patients will only be followed for disease status and survival.

 Pre-treatment PET-CT and pre-treatment dental evaluation preferred, but these will be ordered at the discretion of the treating physician.

## 9.0 Measurement of Response

### 9.4 Tumor Clearance

A primary clinical endpoint of this study is progression-free survival. A patient will be considered to have a complete response if there is no measurable or palpable tumor either on clinical or radiographic (CT-PET scan or MRI) examination assessed within approximately 3 months after the completion of treatment. Complete response will

be defined as complete disappearance of disease (in which case 9.2 will apply to assess relapse) or residual radiographic abnormality (which cannot be safely biopsied) that is not considered to be tumor (in which case section 9.3 will apply to assess progression).

**9.5**                    Local or Regional Relapse

Relapse is defined as reappearance of tumor after complete response. If possible, relapse should be confirmed by biopsy.

**9.6**                    Local or Regional Progression

Progression is defined as an estimated increase in the size of the tumor (product of the perpendicular diameters of the two largest dimensions) of greater than 25%, taking as reference the smallest value of all previous measurements or appearance of new areas of malignant disease.

**9.7**                    Distant Metastasis

Clear evidence of distant metastases (lung, bone, brain, etc.); biopsy is recommended where possible. A solitary, spiculated lung mass/nodule is considered a second primary neoplasm unless proven otherwise.

**9.8**                    Second Primary Neoplasm

Tumor reappearing with the initial and immediate adjoining anatomical region of the primary will be considered local recurrence. Multiple lung nodules/masses are considered distant metastases from the index cancer unless proven otherwise.

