## 6.0 Schema

## 7.0 Study Design

### 7.1 Overview

Patients will receive a single dose of cetuximab 400 mg/m^2 (Day 0). On day 7 (+/- 1 day), a repeat biopsy will be performed. Within approximately 4 days, definitive radiation will begin (70 Gy in 35 fractions to the gross tumor, 50-60 Gy to subclinical target volumes) concurrent with weekly cetuximab 250 mg/m^2. Twelve to 14 weeks following the completion of cetuximab-radiation, patients will undergo standard restaging and treatment, including CT-PET, repeat laryngoscopy and tumor site biopsies. Patients with evidence of persistent tumor may undergo surgical salvage and/or neck dissection.

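### Tumour that persists at the 12-14 week restaging and then stays stable or is resected meets no local or regional event definition, and the logistic option for local recurrence has no time point or rule for deaths

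*Combined protocol and SAP*

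**What the plan says.** Section 9 holds every local or regional event rule:

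- 9.4 splits complete response into two kinds. One is "complete disappearance of disease (in which case 9.2 will apply to assess relapse"). The other is a residual radiographic abnormality not thought to be tumour, which goes to the progression rule. The references there to 9.2 and 9.3 are read here as 9.5 and 9.6, the relapse and progression paragraphs.
- 9.5: "Relapse is defined as reappearance of tumor after complete response".
- 9.6: "Progression is defined as an estimated increase in the size of the tumor" of more than 25% over the smallest earlier value, or new malignant disease.
- 9.8, on second primaries: "Tumor reappearing with the initial and immediate adjoining anatomical region of the primary will be considered local recurrence".

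The protocol expects persistent tumour. In 7.1, 12 to 14 weeks after treatment, "patients will undergo standard restaging and treatment, including CT-PET, repeat laryngoscopy and tumor site biopsies", and "Patients with evidence of persistent tumor may undergo surgical salvage and/or neck dissection". Section 7.5.6 requires biopsy of persistent neck nodes and says that patients with a node initially above 3 cm "who are CT-PET positive at 12-14 weeks post cetuximab-RT will undergo neck dissection". Neither section says what this means for an endpoint. Footnote 2 of the Study Calendar says of follow-up: "Biopsies, labs and imaging studies will be performed as clinically indicated".

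Section 21.3.2 names logistic and Cox regression for local recurrence, PFS and overall survival. It does not assign a model to an outcome, fix a time point for a binary outcome, or say how death without recurrence is handled.

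**The concern.** Section 1.1 aims at a predictor of local control, and 21.4 says the primary objectives compare responders with non-responders. A patient whose tumour never cleared is a non-responder. If that patient counts as having no local recurrence, the outcome looks better than it was and the marker is tested against a mixed group. The trial is single-arm, so no comparator offsets this. If the status is left open, it can be settled after marker results are known.

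The model choice matters for the same outcome. One natural reading of an untimed binary variable is 'ever recurred'. That treats short follow-up and death without recurrence the same as lasting control.

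**Working it through.** **1. Definitions side by side.**

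| Course | 9.5 relapse | 9.6 progression | 9.8 local recurrence |
|---|---|---|---|
| Clears, then returns at the primary site | met | not needed | met |
| Persists, later grows >25% or new disease appears | not met (no complete response) | met | not needed |
| Persists at primary site, stable to end of follow-up | not met | not met | not met (never reappeared) |
| Persists at primary site, resected before growth, no return | not met | not met | not met |
| Persists in neck nodes, stable or removed, no return | not met | not met | not applicable (primary region only) |

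The gap is the last three rows. Section 9.6 does not require a prior complete response, so the second row is covered.

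**2. The plan's own power figure.** Inputs from 21.4: 50 patients, 36 months of accrual, analysis 6 months later, median 22 months (read as median PFS), alpha 0.05 (taken as two-sided). Rate λ = ln 2 / 22 = 0.0315 per month. Follow-up runs from 6 to 42 months, so the chance of an observed event is 1 − [e^(−6λ) − e^(−42λ)] / (36λ) = 1 − (0.8278 − 0.2663) / 1.1342 = 0.505. Expected events: 50 × 0.505 = 25.2. Simulated Cox power is 77-79% at 1.0 SD and 84-86% at 1.1 SD. The stated figure (at least 80% from 1.1 SD) is reproduced, and this point does not dispute it.

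**3. Size of the scoring gap.** One patient is 1/50 = 2 points of a crude proportion; 3, 5 or 10 patients are 6, 10 or 20 points. The documents give no persistence rate.

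**4. Effect of the scoring gap on marker power.** Illustrative simulation, 2,000 runs per scenario, on the 21.4 schedule. Marker hazard ratio (HR) is 2 per SD on recurrence, and recurrence is 50% or 70% of the baseline hazard. Five persisters are assumed, drawn at 5.06 months from patients still event-free and in follow-up.

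| Recurrence share, HR on death | Tracks marker: not counted v counted | Unrelated to marker: not counted v counted |
|---|---|---|
| 50%, HR 1 | 48.6% v 73.8% | 61.5% v 46.8% |
| 50%, HR 2 | 47.0% v 71.8% | 54.1% v 40.6% |
| 70%, HR 1 | 57.8% v 83.4% | 71.9% v 61.4% |
| 70%, HR 2 | 57.6% v 81.0% | 68.0% v 56.7% |

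The sign depends on whether persistence follows the marker, which the documents do not tell us.

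**5. Untimed logistic model.** At the analysis, follow-up depends only on entry date. The chance of an observed PFS event runs from 1 − e^(−6λ) = 17% to 1 − e^(−42λ) = 73%. Only (42 − 24)/36 = 50% of patients could have 24 months of follow-up. Simulation, 4,000 runs, combined median 22 months:

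| Recurrence share of baseline hazard | HR per SD, recurrence / death | 'Ever recurred' logistic | Cause-specific Cox |
|---|---|---|---|
| 50% | 2 / 2 | 31.2% | 60.1% |
| 50% | 2 / 1.5 | 43.8% | 64.7% |
| 50% | 2 / 1 | 57.1% | 66.0% |
| 70% | 2 / 2 | 50.2% | 75.5% |
| 70% | 2 / 1.5 | 58.5% | 77.9% |
| 70% | 2 / 1 | 68.5% | 77.6% |
| 50% | 1 / 2 | 5.8% | 4.6% |
| 70% | 1 / 2 | 5.8% | 5.3% |

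A repeat gave 30-69% v 60-78% for the HR 2 rows and false-positive rates of 5-7% v 5%. In the 50%, 1 / 2 row the median odds ratio drifts to 0.84 (HR 1.00), but the rejection rate barely moves. Follow-up of 24 to 60 months does not remove the loss: 27-78% v 72-89%.

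**6. Tissue.** Section 7.1 lists tumour site biopsies for restaged patients generally and 7.5.6 requires biopsy of persistent nodes, while footnote 2 leaves biopsies to clinical indication. These statements decide who has tissue, and they do not agree.

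**The case against.** A reader might infer that the plan scores these patients as local control. No sentence says so. Local control is an aim in 1.1, is never defined, and is not an outcome in 21.3.2. Having no local recurrence is what a literal reading yields; calling the patients unclassified is equally fair. A rule is needed either way.

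A reader might also infer that all persistent tumour is missed. It is not: 9.6 captures later growth or new disease, and 9.7 captures metastasis. Section 9.4 also identifies these patients as not being complete responders. That stands, but 21.3.2 has no response outcome that would use the distinction.

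Nodal persistence does not bear on local recurrence, which 9.8 ties to the region of the primary. That stands too, so local and regional failure must be kept apart.

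The power contrast in step 4 rests on five assumed persisters who never have a later local event. In the marker-related case, if only half never do, it becomes about 50-69% v 71-85%; if a quarter, 57-76% v 72-85%. These figures cannot support a claim that power is lost.

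On the model, 21.3.2 already names Cox regression, and the sample size rests on it. Nothing says that an untimed logistic model would replace it. The 30% floor needs a marker effect on death as strong as on recurrence, and half the baseline hazard from death. What remains is that the text permits the weaker analysis for a primary-objective outcome.

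**Conclusion.** The concern holds in limited form and is worth fixing. Stable or resected persistent tumour meets no local or regional event rule. Read literally, it counts as no local recurrence in Primary Objective 2, and its PFS status is unspecified. The size is unknown: 2 points of a crude proportion per patient among 50, with marker power moving either way. The case for a scoring rule is correct classification, not power.

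On the model, an untimed logistic analysis costs power on the 21.4 schedule: about 30-69% v 60-78% at HR 2 per SD. This assumes that deaths without recurrence make up 30-50% of the baseline hazard and that the marker HR on death is 1 to 2. A reader might infer many false positives from the logistic option; the rejection rates under no effect on recurrence do not support that.

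**What to change.** For endpoint scoring only, with no change to patient management:

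- In section 9 and 21.3.2, count pathologically confirmed persistent tumour at the primary site at restaging (positive biopsy, or viable tumour in a salvage specimen) as local failure dated at restaging.
- Count confirmed persistent nodal tumour, including viable tumour in a 7.5.6 neck dissection, as regional failure. Report it separately and within a combined local-regional failure endpoint.
- Leave the 9.4 rule on residual radiographic abnormality unchanged.
- Count confirmed persistence as a PFS event at restaging. Add one sensitivity analysis that does not count it, and another that also counts persistence judged clinically or radiographically without tissue.
- Make cause-specific Cox regression the analysis of local and local-regional failure, with death without recurrence as a competing event and cumulative incidence for description.
- Reconcile 7.1 and 7.5.6 with Study Calendar footnote 2 on restaging biopsies.

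The cost is definition and analysis wording, plus case report form fields for restaging and surgical pathology. Reported local control becomes slightly less favourable. Marker power falls if persistence is unrelated to the marker (54-72% to 41-61% in step 4). Tissue may not exist for every patient, which is why the analysis of cases without tissue is needed.

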**10.0**                **Criteria for Discontinuation of Treatment**

In the absence of treatment delays due to adverse events, treatment may continue through completion of concurrent chemoradiotherapy and consolidation chemotherapy or until one of the following criteria applies:

- Local-regional disease progression
- Intercurrent illness that prevents further administration of treatment
- Unacceptable adverse events(s)
- Patient decides to withdraw from the study
- General or specific changes in the patient's condition render the patient unacceptable for further treatment in the judgment of the investigator.

If treatment is interrupted due to a non-dose-limiting adverse event or any reason other than toxicity, such as a holiday, bad weather, or a transportation problem, the duration of therapy will be extended accordingly. If a patient misses a day of radiation and chemotherapy, then the weekly chemotherapy should be delivered the next day and the missed radiation fraction will be given after the completion of planned treatments.

Patients who exhibit local-regional tumor progression will discontinue all study procedures and will be medically managed. For the purposes of the research, they will continue to be followed for toxicity and survival. These patients may be treated with other agents.

